7.4 SAE & AEs Requiring Discontinuation of Study Drug, including Pregnancies

ANY SAE THAT OCCURS AFTER A SUBJECT HAS ENTERED THE STUDY, WHETHER OR NOT RELATED TO STUDY MEDICATION, MUST BE REPORTED TO [REDACTED] IMMEDIATELY (WITHIN 24 HOURS) VIA TELEPHONE OR FACSIMILE. IF INITIALLY REPORTED VIA TELEPHONE, THIS MUST BE FOLLOWED-UP BY A FACSIMILE OF THE WRITTEN SAE REPORT WITHIN 24 HOURS OF THE CALL TO [REDACTED].

Non-serious events that require discontinuation of study medication (including laboratory abnormalities) should be reported to [REDACTED] immediately and within 1 working day.

Subjects who discontinue due to experiencing adverse events should be followed clinically until their health has returned to baseline status or until all parameters have returned to normal. It is expected that the investigator will provide or arrange appropriate supportive care for the subject.

A subject who experiences a severe adverse event related to study drug will be discontinued from the study.

The notification about any serious adverse event should be directed to:

[REDACTED]
[REDACTED]
[REDACTED]
[REDACTED]
[REDACTED]
[REDACTED]

[REDACTED] will report the SAE to the Sponsor:

SPONSOR

[REDACTED]
[REDACTED]
[REDACTED]
[REDACTED]
[REDACTED]
[REDACTED]
[REDACTED]
[REDACTED]
[REDACTED]

7.5 Pregnancy

At the time the Principal Investigator or site personnel becomes aware that a study participant became pregnant during study participation, the Principal Investigator or designee will report the pregnancy immediately by phone and/or by faxing a completed Pregnancy Report to [REDACTED] within 1 business day of being notified of the pregnancy report.

The report will include the following elements:

- Participant (mother's) coded study identifier;
- Date of participant's last menstrual period;
- Total accumulated dose of study treatment administered to date;
- Date of study medication administration.

The investigator will follow the subject until completion of the pregnancy and must assess the outcome in the shortest possible time but not more than 30 days within completion of the pregnancy.

Upon delivery, miscarriage or abortion, the Principal Investigator or designee must forward a follow-up Pregnancy Report with any relevant information on the present condition of the fetus to the [REDACTED], including:

- Mother's coded study identifier(s);
- Gestational age at delivery, miscarriage or abortion;
- Birth weight, gender, length and head circumference, if available;
- Apgar scores recorded after birth, if available;
- Any abnormalities.

If the outcome of the pregnancy **meets the criteria for immediate classification of an SAE** (e.g., spontaneous or therapeutic abortion [any congenital anomaly detected in an aborted fetus is to be documented], stillbirth, neonatal death, or congenital anomaly), the investigator will report the event by phone and by faxing a completed SAE report form to [REDACTED] within 1 working day of being notified of the pregnancy report.

If the trial is completed before the outcome of the pregnancy is known, [REDACTED] will assume the responsibility for following up on the pregnancy. [REDACTED] will contact the investigator or Study coordinator on or around the potential expected date of delivery to follow-up on the outcome of pregnancy and will also check on the status of the infant 8 weeks post-delivery. Upon awareness of the pregnancy outcome and known status of the infant following 8 weeks of delivery, the investigator will complete the applicable pregnancy report forms and fax to [REDACTED] within 1 day of being notified.

7.6 Post Study Adverse Events

Non-serious Adverse Events

Adverse events that are identified at the last assessment visit (or the early termination visit) must be recorded on the AE eCRF with the status of the AE noted. These adverse events must be followed by the investigator until the events are resolved, events determined to be chronic or the subject is lost to follow-up. Resolution means the subject has returned to the baseline state of health or the investigator does not expect any further improvement or worsening of the adverse event.

Serious Adverse Events

Serious adverse events that are identified on the last assessment visit (or the early termination visit) must be recorded on the AE eCRF page and reported to Perrigo according to the procedures outlined above. Subjects with unresolved previously reported serious adverse events, or any new serious adverse events identified on the last assessment visit, should be followed by the investigator until the events are resolved, or the subject is lost to follow-up. Resolution means the subject has returned to the baseline state of health or the investigator does not expect any further improvement or worsening of the adverse event. The investigator should continue to report any significant follow-up information to Perrigo up to the point that the event has resolved. Any serious adverse event reported by the subject to the investigator that occurs after the last assessment and is determined by the investigator to be reasonably associated with the use of the study drug, should be reported to Perrigo.

8. STATISTICAL ANALYSIS

The sections that follow highlight sample size determination and the planned analyses for this study. A statistical analysis plan (SAP) that describes the statistical methods, models, hypotheses, and subject populations to be analyzed will be prepared separately from this protocol. The SAP will be completed and approved before locking the database and unblinding the study and will serve as a companion to the protocol and the *de facto* documentation of the proposed statistical evaluation. The SAP will be completed and finalized prior to breaking the blind.

8.1 Statistical Methods

Analysis Populations

The following populations are defined for the purpose of analyses:

- Intent-to-Treat (ITT) (safety population): Any subject who was randomized, received and used study medication.
- Modified Intent-to-Treat (mITT): Any subject who met the inclusion/exclusion criteria (including a positive baseline bacteriological culture), was randomized, received and used the study medication, and returned for at least one post-baseline efficacy assessment.
- Per Protocol (PP): Any subject who:
 - met inclusion/exclusion criteria (including a positive baseline bacteriological culture),

- was randomized, received and used study medication,
- met the protocol criteria for compliance [REDACTED]
[REDACTED]
- completed Visit 4/Day 17 evaluations within the designated window [REDACTED] OR was discontinued from the study due to treatment failure, and
- had no significant protocol violations that could have interfered with the administration of the treatment or the precise evaluation of treatment efficacy.

[REDACTED]
[REDACTED]
■ [REDACTED]
■ [REDACTED]
■ [REDACTED]
■ [REDACTED]
[REDACTED]
[REDACTED]

Only subjects with a baseline bacteriological culture from the target lesion that is positive for *S. aureus* and/or *S. pyogenes* will be included in the PP and mITT populations for the efficacy analysis. Subjects with a negative baseline culture will be excluded from the PP and mITT populations but included in the ITT population.

Planned Analysis

The safety analysis will be performed for the ITT subjects. The efficacy analysis will be conducted on both the PP and the mITT populations. Two-sided hypothesis testing will be conducted. Resulting p-values less than 0.05 will be considered statistically significant. No adjustments of p-values for multiple comparisons will be made. No interim analyses are planned. SAS software will be used for all data analyses and tabulations.

The treatment response will be summarized by treatment group.

[REDACTED]
[REDACTED]
[REDACTED]
[REDACTED]

Sample Size Considerations

[REDACTED]
[REDACTED]

A thick black horizontal bar is positioned at the bottom of the slide, spanning most of the width. It is likely a decorative element or a placeholder for content.

A series of six horizontal black bars of increasing length, starting from a short bar on the left and ending with a long bar on the right, suggesting a sequence or progression.

Efficacy Measures and Analysis

Clinical Endpoints

The primary efficacy endpoint is the proportion of subjects in each treatment group with clinical cure, defined as a SIRS score of 0 for all signs and symptoms at Visit 4/Follow-up (7 days after the end of treatment). Secondary efficacy endpoints are the proportion of subjects with clinical cure at Visit 3/End of Treatment, bacteriological cure (defined as elimination of *S. aureus* and *S. pyogenes* or response was such that no culture material was available and therefore evidence of pathogen eradication) at Visit 3/End of Treatment, and bacteriological cure at Visit 4/Follow-up.

Equivalent efficacy

The clinical equivalence of the test and reference treatments will be based on the proportions of subjects with clinical cure at Visit 4/Day 17 (Follow-up, 7 days after end of treatment).

The hypothesis tested for clinical equivalence between test and reference will be:

$H_0: p_T - p_R < -0.20$ or $p_T - p_R > 0.20$ versus

$$H_A: -0.20 \leq p_T - p_R \leq 0.20.$$

Where p_T and p_R were the proportions of subjects with clinical cure at Visit 4/Day 17 for the Test and Reference products, respectively. The Test product would be considered to be clinically equivalent to the Reference product if the 90% confidence interval (CI) of the difference between their proportions of subjects with clinical cure, calculated by the Wald's method with Yates' continuity correction, is contained within the limits -20.0% to +20.0%. Rejection of the null hypothesis would support the conclusion of therapeutic equivalence between the Test and Reference products for the primary efficacy variable.

Analysis in the PP population will be considered definitive and those in the mITT population will be considered supportive.

Superiority

The test of superiority of each active treatment over vehicle will be based on the proportions of subjects in each treatment group with clinical cure at the Visit 4/Day 17 [REDACTED]

Protocol No: PRG-NY-19-002

The hypotheses tested for superiority of the test and reference products over Vehicle will be:

$H_0: p_T \leq p_V$ versus $H_A: p_T > p_V$

$H_0: p_R \leq p_V$ versus $H_A: p_R > p_V$

Where p_T , p_R , and p_V are the proportions of subjects with clinical cure at the Visit 4/Day 17 for the Test, Reference, and Vehicle products, respectively. The tests will be conducted independently for the Test product and the Reference product using two-sided, $\alpha = 0.05$, continuity-corrected Z-tests. Superiority would be established if the proportion of subjects with clinical cure at the Visit 4/Day17 in the active treatment group is significantly greater ($p < 0.05$) than that in the Vehicle group. Rejection of the null hypothesis would support the conclusion of superiority of the Test and Reference products over the Vehicle for the primary efficacy variable.

Superiority analyses in the mITT population will be considered definitive and those in the PP population will be considered supportive.

The same tests/methods, including the missing data imputation methods, as for the primary analyses will be conducted for the secondary analyses.

Safety and Adverse Events Analysis

The frequency and percent of subjects with adverse events will be summarized by MedDRA system organ class and preferred term and by severity and relationship to study drug for all three treatment groups. [REDACTED]

[REDACTED]. The comparable safety of the Test and Reference treatments will be evaluated by statistical comparison of the proportion of subjects who reported any adverse events. Safety comparisons will be performed on the ITT (safety) population.

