2.2 Safety

Safety of the test and reference products will be compared by evaluating the nature, severity and frequency of their adverse event profiles. All adverse events that occur during the study will be recorded whether or not they are considered to be related to the study medication. Descriptions of reactions or complaints will include the approximate date of onset, the date the adverse event ended, the severity of the adverse event, and the outcome. Comparisons between the treatment groups will be made by tabulating the frequency of subjects with one or more adverse events (classified into MedDRA terms) during the study. Pearson's Chi-Square test or Fisher's Exact test, whichever is most appropriate, will be used to compare the proportion of subjects in each treatment group with any adverse event. [REDACTED]

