## 5 Planned Analyses

### 5.1 Methodological Considerations

Tables will have columns corresponding to or be stratified by the treatment groups.

All data will be listed by treatment group, subject and visit/time point where appropriate. The total number of subjects under the stated population (N) will be displayed in the header of summary tables. Efficacy data will be tabulated by site and if obviously inconsistent discrepancies will be observed with the results across all sites, then these differences will be explored and addressed in the final study report.

Data will be summarized using descriptive statistics for continuous variables. Unless otherwise specified, descriptive statistics will include number of subjects, mean, standard deviation, minimum, median and maximum. The statistic “Missing” will also be presented as the number of missing entries/subjects, if any at that visit/timepoint, and presented as a summary statistic only when non-zero. The minimum and maximum statistics will be presented to the same number of decimal places as the original data. The mean and median will be presented to one more decimal place than the original data, whereas the standard deviation will be presented to two more decimal places than the original data.

Categorical variables will be summarized by frequency (n) and percentage (%). Percentage will be obtained as  $(n/N) * 100$ . Unless otherwise stated, all percentages will be expressed to one decimal place.

Study days will be calculated as follows:

- For events or findings on or after the date of the first study treatment:
  - o Study Day = Date of the event or finding – Date of the first treatment + 1

- For events or findings prior to the date of the first study treatment:
  - o Study Day = Date of the event or finding – Date of the first treatment
- All dates will be displayed in DDMMYY format.

Two-sided hypothesis testing will be conducted for all the tests. P-values less than 0.05 will be considered statistically significant. No adjustments of p-values for multiple comparisons will be made. No interim analyses are planned.

All statistical analysis will be conducted using SAS® version 9.4 or higher (SAS® Institute, Cary, North Carolina).

[REDACTED]

[REDACTED]

[REDACTED]

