#### Adverse Events

Adverse events (AEs) will be coded in MedDRA, version 22.0. Treatment-Emergent Adverse Event (TEAE) is defined as any AE occurs on or after application of the first dose of study drug. Number and percent of subjects reporting TEAEs will be tabulated by treatment group. Summary of TEAEs will be presented by body system and preferred term for the ITT population, and further by severity and relationship to study medication. Most common TEAEs will include those reported by 5% or more subjects for any treatment group will be summarized by preferred term. In the summaries of incidence rates (frequencies and percentages), severity and relationship to study drug, subjects who report more than one event that are mapped to the same preferred term will be counted only once under the strongest severity and relationship, accordingly. The difference between Test and Reference treatments with regard to severity and

frequency of their dermatological adverse events will be statistically evaluated using Chi-Square or Fisher's exact test to compare the proportions of subjects of the two active treatment groups who report any TEAE.

Treatment-Emergent Serious Adverse Events (TESAEs) will be discussed within the clinical study report. TEAEs, TESAEs and TEAEs that led to treatment interruption temporarily or treatment discontinued permanently will be presented in data listings.

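### Comparable safety of Test and Reference rests on a test of no difference in any-adverse-event rates; the readable plan gives no risk difference, interval or other inferential criterion

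*Protocol*

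**What the plan says.** The study objective, in both documents, includes comparing the safety profiles of the Test and Reference products.

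- **Protocol 8.1, Safety and Adverse Events Analysis:** "The comparable safety of the Test and Reference treatments will be evaluated by statistical comparison"; what is compared is the share of subjects reporting any adverse event. The comparison is made in the ITT (safety) population.
- **Protocol 2.2, Safety:** "Pearson's Chi-Square test or Fisher's Exact test, whichever is most appropriate, will be used to compare the proportion of subjects in each treatment group"; the outcome here is again the occurrence of any adverse event.
- **SAP 5.8, Adverse Events:** the Test–Reference comparison is made "using Chi-Square or Fisher's exact test to compare the proportions of subjects of the two active treatment groups who report any TEAE".
- **SAP 5.1:** "Two-sided hypothesis testing will be conducted for all the tests", and "P-values less than 0.05 will be considered statistically significant".

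Both documents also plan descriptive tables of adverse events by system organ class, preferred term, severity and relationship to study drug. SAP 5.8 adds a table of events reached by 5% or more of any group, discussion of serious events in the study report, and listings of events leading to interruption or discontinuation.

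For efficacy, Protocol 8.1 and SAP 5.7.1 ask the same kind of Test-versus-Reference question. They answer it with a 90% confidence interval on the difference in cure proportions, judged against limits of ±20 percentage points.

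**The concern.** The question is whether two products are comparable in safety, but the named method tests the hypothesis that they do not differ. Failing to reject that hypothesis is not evidence for it. The fewer the subjects or events, the easier a non-significant result is to obtain, so weak data look reassuring. The efficacy analysis avoids this by judging an interval for the difference against stated limits. The safety analysis has no counterpart in the readable text.

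At stake is the strength of the safety statement in the study report. A p-value above 0.05 does not tell the reader how large an excess of adverse events on the Test product the data still allow.

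**Working it through.** **1. Is there a stated figure to reproduce?** No. Sample size and allocation are redacted. The readable text gives no power, margin or assumed rate for the safety comparison. Protocol section 7 gives only single-term rates for the marketed cream (headache 1.7%, rash 1.1%, nausea 1.1%), not an any-event rate.

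**2. Inputs**
- From the documents: two independent proportions (Test, Reference), chi-square or Fisher test, two-sided, 0.05.
- Assumed: n = 150, 250 or 400 treated subjects per active arm, 1:1; true any-event rates, Test v Reference, of 5% v 2.5%, 10% v 5% and 20% v 10%.

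**3. How often would the test be non-significant although the Test rate is truly double?** With x_T and x_R the numbers of subjects with an event and p̄ = (x_T + x_R)/(2n), the Pearson statistic is

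z = |x_T − x_R|/n ÷ √[2p̄(1 − p̄)/n].

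The test is significant if z > 1.96. Power is the sum of Bin(x_T; n, p_T) × Bin(x_R; n, p_R) over all pairs with z > 1.96, by exact enumeration without continuity correction. The non-significant share is 1 − power.

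| True rates, Test v Reference | n = 150 | n = 250 | n = 400 |
|---|---|---|---|
| 5% v 2.5%: power | 0.195 | 0.312 | 0.461 |
| non-significant | 80% | 69% | 54% |
| 10% v 5%: power | 0.370 | 0.572 | 0.776 |
| non-significant | 63% | 43% | 22% |
| 20% v 10%: power | 0.686 | 0.887 | 0.980 |
| non-significant | 31% | 11% | 2% |

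(The first cell is 1 − 0.1954 = 0.8046 before rounding.) Fisher's test misses more: at 200 per arm and 10% v 5%, exact power is 47% for Pearson and 41% for Fisher.

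**4. What would an interval add?** The 95% half-width at true rates of 10% and 5% is 1.96 × √[(0.10 × 0.90 + 0.05 × 0.95)/n]:
- n = 150: 5.9 points
- n = 250: 4.6 points
- n = 400: 3.6 points

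**5. One illustrative result.** Assume 200 per arm, with 33 Test and 20 Reference subjects having an event.
- Difference: 33/200 − 20/200 = 0.165 − 0.100 = 0.065.
- Pooled proportion: 53/400 = 0.1325. Standard error: √(0.1325 × 0.8675 × 2/200) = 0.0339. z = 0.065/0.0339 = 1.92, p = 0.055: non-significant.
- Wald 95% CI: 0.065 ± 1.96 × √(0.165 × 0.835/200 + 0.100 × 0.900/200) = 0.065 ± 1.96 × 0.03375, that is −0.1 to 13.1 points.

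The test alone returns non-significant. The interval shows that the data are compatible with an excess of about 13 points on Test.

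**The case against.** **No decision rule is written.** A reader might infer that the plan treats p ≥ 0.05 as proof of comparable safety, or that a real excess will be reported as comparability. The documents do not say so. For efficacy they state explicitly when the products will be considered equivalent; for safety there is no such sentence. What stands is narrower: the protocol links comparable safety to this statistical comparison, and the readable text supplies no other inferential criterion.

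**The test is not the whole safety assessment.** This is correct. The descriptive tables will show both arms' percentages, so the point difference can be worked out by eye. They are described as counts and percentages, however, with no measure of uncertainty on the difference.

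**Redacted or missing text may hold the criterion.** Protocol text immediately before the sentence in 8.1 and directly after the test in 2.2 is redacted. The SAP's safety table shells are listed in its contents but not supplied. A difference or interval there cannot be excluded. The adverse-event paragraphs of SAP 5.8, however, show no redaction and contain only the test.

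**The size depends on assumptions.** It does. With a 10% Reference rate, a doubling is usually detected at 250 or more per arm. The point of principle does not depend on arm size.

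**An interval without a margin still sets no criterion.** This is true if a formal conclusion of comparability is wanted. It is no obstacle if the comparison is labelled descriptive.

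**Conclusion.** The point holds in a limited form: the only inferential method named for comparable safety is a test of no difference, which cannot support comparability, and no interval for the difference appears in the readable text.

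Under the assumed arm sizes, the chance that Pearson's test misses a true doubling ranges from about 80% (5% v 2.5%, 150 per arm) to 2% (20% v 10%, 400 per arm). It matters most where adverse events are uncommon. These figures rest wholly on assumed arm sizes and rates.

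The consequence is possible over-interpretation of the safety statement. Safety is part of the objective but is not among the efficacy endpoints in Protocol 2.1, and the primary equivalence and superiority conclusions are untouched. This is a cheap improvement, not a flaw that threatens the trial.

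**What to change.** In SAP 5.8 and Protocol 8.1:

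1. Report the Test-minus-Reference difference in the proportion of subjects with any TEAE, with a 95% confidence interval (Newcombe, or exact if counts are sparse), in the ITT (safety) population.
2. State that comparability is described from this interval, especially its upper limit, and that a non-significant test is not evidence of comparability.
3. Keep the chi-square or Fisher p-value, labelled descriptive.
4. Label the whole comparison descriptive; no safety margin is then needed. Intervals for each active product against vehicle are optional.

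While editing, reconcile the variable: SAP 5.8 introduces the comparison as one of dermatological events but then tests any TEAE, and Protocol 8.1 refers to any adverse event.

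The cost is a few sentences and a risk-difference request in PROC FREQ, a procedure and option the SAP already uses for cure. No extra subjects or data are needed. The downside is that a wide interval may make the safety statement less favourable.
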